8.2.6. Time to peripheral capillary oxygen saturation (SpO_2) $\geq 94\%$ on room air

The time from baseline to achieving $\text{SpO}_2 \geq 94\%$ on room air will be calculated for each subject. Two summaries will be provided:

- All subjects treated with USB002 vs. all placebo subjects
- USB002 subjects vs. placebo subjects by cohort. That is, comparing between two treatment groups within each cohort (dose level)

All data will be listed.

8.3. Secondary Outcomes

8.3.1. All-cause mortality at Day 60.

All death data will be listed. If data applicable, the death rate at Day 60 will be summarized by total treatment groups, and by cohort and treatment group.

8.3.2. Number of ventilator-free days

The number of ventilator-free days (defined as the number of days between Day 1 and Day 28 that subjects are both alive and free of mechanical ventilation) will be summarized by total treatment groups, and by cohort and treatment group, if data applicable.

All Mechanical Ventilation Status data will be listed.

Total MV duration days will be listed and summarized.

8.3.3. Proportion of subjects weaned from mechanical ventilation through Day 28

The number of subjects who were on MV and then weaned from MV through Day 28 will be counted and the proportion of those subjects out of all subjects applied MV will be summarized.

8.3.4. Proportion of subjects progressing from non-invasive (at baseline) to mechanical ventilation.

The number of subjects who progressed from non-invasive (at baseline) to MV will be counted and the proportion of those subjects out of all subjects were not on MV at baseline will be summarized.

8.3.5. Time to Progression (TTP) from non-invasive (at baseline) to mechanical ventilation.

Time to Progression (TTP), i.e., time from first treatment with study medication to MV will be calculated. If enough data applicable, the outcome will be summarized.

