4.3. Secondary Endpoints

Secondary endpoints include:

- All-cause mortality at Day 60.
- Number of ventilator-free days (defined as the number of days between Visit 1/Day 1 and Day 28 that subjects are both alive and free of mechanical ventilation [MV]; freedom from MV is further defined as free from MV for at least 48 hours after extubation).
 - In the case of repeated MV, duration of MV will be summed for the purposes of calculation. In the case of tracheostomy, the same criteria apply.
- Proportion of subjects weaned from mechanical ventilation through Day 28 (defined as free from MV for at least 48 hours after extubation. In the case of tracheostomy, the same criteria will apply). This applies only to subjects on mechanical ventilation at baseline.
- Proportion of subjects progressing from non-invasive (at baseline) to mechanical ventilation. This applies only to subjects not on mechanical ventilation at baseline.
- Time to progression (TTP) from non-invasive to mechanical ventilation.
 - In the case of repeat admission to hospital and/or ICU within the first 28-days, the time from first treatment with study medication will be used to calculate TTP to MV.
- Number of days of vasoactive agent usage (defined as use of a vasoactive agent for 6 hours or more within any 24-hour period).
- Time (days) to hospital discharge.
- Changes in Ordinal Scale for Clinical Improvement (OSCI) status (see Appendix 1) from Visit 1/Day 1 to Day 28, defined as 1) time to change and 2) proportions of subjects, with 1-point and 2-point clinical status changes utilizing a time-to-event analysis from time of start of infusion (Visit 1/Day 1) of study medication to Day 28 for the time to change analysis between active and placebo groups.

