7.2. Calculated Outcomes

The following are key endpoints derived from data captured at the sites via the EDC system. Complete documentation of the calculations and data manipulation required to go from the CRF database to the analysis database are contained in the companion documents – SDTM Programming Specification File (SDTM Spec) and ADaM Programming Specification File (ADaM Spec).

Outcome	Calculation	Comment
Study Day	= the days from Day 1 (Date of the First Study Infusion) to the event date	
Time in Trial (days)	= Study completion/withdrawal date – date of informed consent date + 1 day	
Time on Treatment	= Date of last infusion – Date of first infusion + 1	
Baseline value	= Value reported prior to the first study treatment	If multiple values collected prior to the first infusion, non-missing value closest to the date/time of the first infusion is considered as baseline value
Change from Baseline	= Value collected at time point (Visit) – Baseline value	
BMI	= $10000 * (\text{Weight in kg}) / (\text{Height in cm})^2$	Value will be rounded to keep one decimal point
Treatment Emergent Adverse Event (TEAE)	= No, if onset date/time AE is before the date/time of the first study infusion = Yes, otherwise	According to conservative rule, all AEs that cannot be determined as started before the first study infusion will be considered as TEAE

Outcome	Calculation	Comment
Time from baseline to achieving $\text{SpO}_2 \geq 94\%$ on room air	= Date of first achieving $\text{SpO}_2 \geq 94\%$ on room air – Date of first infusion + 1 = null if the subject did not achieve $\text{SpO}_2 \geq 94\%$ till study termination	
Number of ventilator-free days	= the number of days between Day 1 and Day 28 that subjects are both alive and free of mechanical ventilation	
Weaned from MV (Yes/No)	= Yes, if the subject was on MV and then weaned from MV through Day 28 = No, if the subject was on MV and kept using MV till Day 28 = null, if the subject did not use MV from Day 1 to Day 28	
Progressed to MV (Yes/No)	= Yes, if the subject progressed from non-invasive (at baseline) to MV on/before Day 28 = No, if the subject was keeping non-invasive till Day 28	
Time to Progression (TPP)	= First MV date – Date of first infusion + 1 = null, if the subject was keeping non-invasive till Day 28	
Time to hospital discharge	= Hospital discharge date – Study Day 1 + 1 = null if the subject was staying in hospital till Day 28	

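### The SAP derives ventilator-free days without the 48-hour post-extubation condition in its own endpoint definition, and its weaning derivation does not restate that condition

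*SAP*

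**What the plan says.** The endpoint definitions, which are the same in protocol 2.1.2 and SAP 4.3:

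- Ventilator-free days are days from Day 1 to Day 28 alive and free of MV, with the qualifier that "freedom from MV is further defined as free from MV for at least 48 hours after extubation". A further rule reads "In the case of repeated MV, duration of MV will be summed for the purposes of calculation", and tracheostomy follows the same criteria.
- Weaning has the same test: "Proportion of subjects weaned from mechanical ventilation through Day 28 (defined as free from MV for at least 48 hours after extubation". It applies only to subjects on MV at baseline.

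The derivations and analyses:

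- SAP 7.2 computes ventilator-free days as "the number of days between Day 1 and Day 28 that subjects are both alive and free of mechanical ventilation". SAP 8.3.2 repeats this as a definition: "defined as the number of days between Day 1 and Day 28 that subjects are both alive and free of mechanical ventilation". Neither has a duration condition.
- SAP 7.2 codes weaning as "Yes, if the subject was on MV and then weaned from MV through Day 28" and "No, if the subject was on MV and kept using MV till Day 28". SAP 8.3.3 says "The number of subjects who were on MV and then weaned from MV through Day 28 will be counted". Neither gives a number of hours.

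Three other places bear on the point. Protocol 7.2.1 treats death before Day 28 as an unfavourable outcome for the weaning analysis, equivalent to being on MV; SAP 7.2 and 8.3.3 do not mention this. SAP section 6, which lists departures from the protocol, covers Part 2, the OSCI timing analysis and vasoactive agents, but neither ventilator endpoint. SAP 7.2 says that full calculation details are in the SDTM and ADaM programming specifications, which are not among the documents.

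**The concern.** The 48-hour condition separates a successful extubation from a failed one. Without it, a subject taken off the ventilator for a day and then re-intubated collects a ventilator-free day that the endpoint was written to withhold. The same holds for a subject who is extubated and dies within two days. SAP 8.3.2 does not merely point back to 4.3. It states a definition of its own, and a shorter one, so the SAP contains two definitions of the same endpoint.

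Enrolment stopped at 21 subjects and SAP 7.4 rules out inference, so the descriptive summaries are the whole efficacy result. SAP 8.1 and 8.3.2 also call for summaries within each cohort, where the design gives three subjects per arm. At that size the coding of one subject is visible in the result. Ventilated patients can enter the trial (protocol 4.1, inclusion criterion 5), so the endpoints can apply.

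**Working it through.** The plan states no figure for these endpoints, so there is none to reproduce. The check compares the two rules on assumed ventilation histories, counted in whole days.

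**Inputs.** Window of Days 1 to 28 and the 48-hour condition (protocol 2.1.2, SAP 4.3); literal rule (SAP 7.2, 8.3.2). The histories are assumptions; the documents give none.

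**Rules.**

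- Literal rule: VFD = number of days d in 1 to 28 on which the subject is alive and not on MV.
- 48-hour rule: the same count, except that an MV-free run after extubation earns nothing if it lasts less than 2 days and ends in re-intubation or death. All days of a qualifying run count.

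**Ventilator-free days.**

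| Assumed history | Literal | 48-hour rule | Difference |
|---|---|---|---|
| A. MV Days 1–9, off Day 10, MV Days 11–28 | 1 | 0 | 1 |
| B. MV to Day 28 except for single days off on Days 6, 11 and 16 | 3 | 0 | 3 |
| C. MV Days 1–9, off Day 10, dies Day 11 | 1 | 0 | 1 |
| D. MV Days 1–9, off Day 10, MV Days 11–19, off Days 20–28 | 1 + 9 = 10 | 9 | 1 |
| E. MV Days 1–9, then off to Day 28 | 28 − 9 = 19 | 19 | 0 |

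The literal rule adds 1 day for each one-day failure. A clean extubation is unaffected.

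The last row depends on one reading. Protocol 2.1.2 and SAP 4.3 do not say whether the first 48 hours of a successful extubation count. If credit began only after 48 hours, E would be 19 − 2 = 17, and the two rules would then differ for successful extubations too.

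**Weaned status.**

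| History | SAP 7.2 as written | With the SAP 4.3 test |
|---|---|---|
| A, B | Ambiguous: off MV at some point, but ventilated at Day 28 | No |
| C | Does not meet the No condition, so could be Yes | No |
| D, E | Yes | Yes (off MV for 9 and 19 days) |

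C is the clearest case. The subject was not ventilated to Day 28, so the No line does not apply. Both the 48-hour test and the protocol's death rule would code No.

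**Effect of one misclassified subject on the weaned proportion.** Shift = 100/n percentage points, where n is the number of ventilated subjects in the denominator:

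- n = 2: 100/2 = 50
- n = 3: 100/3 = 33.3
- n = 6: 100/6 = 16.7

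The documents do not give n; these values show the range.

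**The case against.** The best reply is that the 48-hour rule is in the SAP already. Section 4.3 states it, the later sections may be shorthand, and a programmer could apply 4.3 or find the rule in the ADaM specification. This stands to the extent that nobody can say from these documents how the data were programmed. It does not remove the conflict: 8.3.2 offers its own definition, section 6 is silent, and an unseen file cannot settle which definition the SAP intends. Nor is it safe to assume that 7.2 silently inherits section 4. For the SpO2 endpoint, SAP 4.2 requires a response sustained for 48 hours, while the calculation in 7.2 uses the date of first achievement.

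On weaning the reply is stronger. SAP 4.3 defines the term, and 7.2 and 8.3.3 use it without redefining it, so the test may be read as carried over. A re-intubated subject ventilated to Day 28 may well be coded No. A reader might infer that any extubation lasting a few hours counts as weaning; the text does not establish that. The death rule in protocol 7.2.1 also sits beside the Fisher's exact tests, while Part 1 efficacy is to be descriptive and detailed in the SAP, so its reach into this analysis could be argued. Case C fails the 48-hour test in SAP 4.3 without it.

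The modest consequence is also fairly argued: this is a descriptive secondary endpoint in 21 subjects, and MV status is listed by subject, so a reader of the listings may see failed extubations.

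**Conclusion.** The point holds as an undeclared inconsistency between the endpoint definition and its derivation. For ventilator-free days the consequence follows from the literal text: about 1 extra day for each one-day failed extubation, or for an extubation followed by death after one day off. For weaning, the derivation leaves the test unstated. It could give a wrong Yes after death within 48 hours of extubation and is ambiguous after re-intubation. One such error moves the proportion by 100/n points.

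Three stronger inferences are not supported:

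- A loss of two days per failure. The whole-day histories show one; more would depend on how part-days are counted.
- A bias towards the arm with more extubation attempts. The excess follows failed extubations, not attempts, and nothing in the documents suggests that the arms differ in either.
- A definite shift of 33 points. It needs exactly three ventilated subjects in the denominator, and that number is not given.

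The conclusion rests on reading SAP 7.2 and 8.3.2 literally, on assumed histories, and on counting all days of a qualifying MV-free period. Only ventilated subjects are affected. It merits correction but does not threaten the trial's main safety purpose.

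**What to change.** In SAP 7.2, 8.3.2 and 8.3.3, carry over the definition in SAP 4.3:

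- Count a day after extubation as ventilator-free only if it lies within an MV-free period of at least 48 hours. State that all days of a qualifying period count.
- Sum repeated MV episodes and apply the same criteria to tracheostomy, as 4.3 says.
- Code weaned as Yes only after at least 48 hours free from MV, and code death before Day 28 as No, following protocol 7.2.1.
- State how an extubation less than 48 hours before the end of Day 28 is handled.
- While editing 8.3.3, reconcile its denominator (all subjects who received MV) with 4.3 (subjects on MV at baseline).

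If the shorter definition is intended, declare and justify it in section 6 instead.

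The cost is SAP wording and a derivation from MV episode records. The SAP already plans to list MV status and summarize total MV duration, so no new collection should be needed. The documents do not show whether stop times are recorded to the hour. If only dates exist, the SAP should state a whole-day convention for the 48-hour test.

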8.3.6. Time to hospital discharge

Total days from Day 1 to hospital discharge will be listed and summarized.

8.3.7. Change of OSCI status from Day 1 to Day 28

For each subject, following outcomes will be calculated:

- Days from baseline to the date with OSCI score decreased 1-point from baseline
- Days from baseline to the date with OSCI score decreased 2-point from baseline
- OSCI score change from baseline to Day 28
- Achieving 1-point decrease of OSCI score at Day 28 (Yes/No)
- Achieving 2-point decrease of OSCI score at Day 28 (Yes/No)

These outcomes will be summarized.

All OSCI data will be listed.

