### 5.3 Other Assays or Procedures

Other assays or procedures include:

- Pregnancy test (for females of childbearing potential).
- OSCI (Appendix 1);
  - In addition to study required OSCI status collection, any additional OSCI assessments conducted during the study will also be collected.
- SBT (Appendix 2);
- Chest X-ray (required at screening only);

- 12-lead ECG to include HR and QRS intervals, QT/QTcF/QTcB; Correlation of QT values using Fridericia's formula;
- Vitals to be captured daily; and during the infusion period at a minimum of every 8 hours. Vitals to include systolic and diastolic BP, HR, RR and temperature;
  - If BP changes significantly post start of infusion, mean arterial pressure will be collected at 15-minute intervals, until resolution;
- Weight measured at screening only;
- Study-required respiratory assessments (first and last assessments can be based on 24 hour clock or from infusion time):
  - Arterial Blood Gas (ABG): If multiple assessments are conducted daily, the first and last assessment of the day will be collected; missed ABGs do not qualify as deviations,
  - $\text{FiO}_2$  (%) – The highest value in a 24-hour period to be recorded in the event of multiple daily assessments,
  - $\text{PaO}_2/\text{FiO}_2$  ratio, the  $\text{PaO}_2$  value to be obtained from the ABG when performed,
  - Respiratory rate (breaths/min) – The highest value in a 24-hour period to be recorded in the event of multiple daily assessments,
  - $\text{SpO}_2$  (%) – The lowest value in a 24-hour period to be recorded in the event of multiple daily assessments.

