#### **Day 16**

- Vitals;
- Respiratory assessments per Section 5.3;
- SBT and at any time that weaning criteria is met;
- OSCi assessment;
- AEs;
- Concomitant medications.

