#### **Days 18, 21, 24, 28**

- OSCi assessment (Day 28);
- AEs;
- Laboratory (chemistry, hematology, coagulation and urinalysis per Section 5.2) (Day 21 and Day 28 with urinalysis at Day 28)
- Concomitant medications;
- Follow-Up (Telemed) (Day 28).

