**5.4.4 End of Treatment or Early Termination of Treatment**

Subjects completing the study up to Visit 5 (in Part 1) or Day 16 (in Part 2) will have End of Treatment procedures completed at Visit 5 (in Part 1) or Day 16 (in Part 2). For subjects discharged prior to Visit 5 (in Part 1) or Day 16 (in Part 2) or where treatment is terminated early, for any reason, all attempts will be made to conduct the End of Treatment (Visit 5 or Day16) procedures (See Tables 2 and 3). End of Treatment (Visit 5 or Day16) procedures may be conducted during the 24-hour observation period.

See Section 5.4.2 Visit 5 (Part 1) and Section 5.4.3 Day 16 (Part 2).

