**5.4.5 Hospital Discharge Prior to Day 28**

If a subject is discharged from hospital earlier than Day 28, Telemed visits will be conducted once a week until Day 28, with the first occurring approximately 7 days after discharge. The Day 28 and Day 60 Telemed visits will occur on Days 28 and 60, respectively, regardless of when the subject is discharged from hospital and the timing of their previous weekly Telemed visits. Part 1 subjects discharged prior to Day 28 will not return to the site for visits (may apply to any of Days 7, 9, 12, 14, 16, 18, 21, or 24, depending on day of discharge) or undergo the procedures regularly scheduled for those visits. Part 2 subjects discharged prior to Day 28 will not return to the site for visits (may apply to Days 18, 21, or 24, depending on day of discharge) or undergo the procedures regularly scheduled for those visits.

Data from the Telemed visits post-discharge will be captured in the EDC.

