Achieving 1-point OSCI Decrease at Visit (Yes/No)	= Yes, if OSCI at visit – OSCI at Day 28 (or End of Treatment) ≥ 1 = No, OSCI at visit – OSCI at Day 28 (or End of Treatment) < 1 = null, if OSCI at Day 1 and/or at visit were missing	
Time to Achieving 1-point OSCI decreasing	= Date of first achieving 1-point OSCI decreasing – Study Day 1 + 1 = null if never achieving 1-point decreasing	

Outcome	Calculation	Comment
Achieving 2-point OSCI Decrease at Visit (Yes/No)	= Yes, if OSCI at visit – OSCI at Day 28 (or End of Treatment) ≥ 2 = No, OSCI at visit – OSCI at Day 28 (or End of Treatment) < 2 = null, if OSCI at Day 1 and/or at visit were missing	
Time to Achieving 2-point OSCI decreasing	= Date of first achieving 2-point OSCI decreasing – Study Day 1 + 1 = null if never achieving 2-point decreasing	

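### In Part 1, a subject discharged after Visit 5 with no OSCI decrease yet recorded has no required score until the Day 28 contact, so the SAP can date the improvement to about Day 28 whatever the discharge day

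*SAP*

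**What the plan says.** SAP 8.3.7 lists, for each subject, "Days from baseline to the date with OSCI score decreased 1-point from baseline" and the same for 2 points, and says these outcomes will be summarized. SAP 7.2 computes the time from "Date of first achieving 1-point OSCI decreasing", less Study Day 1, plus 1, and leaves it null if the decrease is never achieved. Neither section uses the discharge date. SAP 5.3 rules out imputation. SAP 6.1 confines the analysis to Part 1.

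For Part 1, Protocol 5.4.2 lists OSCI ("OSCi assessment") at Visit 5 and again on Day 16. In the block for Days 18, 21, 24 and 28 it is assigned to Day 28 only. After discharge, Protocol 5.4.5 states that "Part 1 subjects discharged prior to Day 28 will not return to the site for visits", and this covers Days 7 to 24 and the procedures due on those days. Weekly Telemed calls replace the visits. Their content is not specified beyond "Data from the Telemed visits post-discharge will be captured in the EDC". The Day 28 call has a window of 3 days either side (Table 2, footnote 6).

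Two provisions work the other way. Protocol 5.3 says: "In addition to study required OSCI status collection, any additional OSCI assessments conducted during the study will also be collected". Protocol 5.4.4 says that, for discharge before Visit 5 or early end of treatment, "all attempts will be made to conduct the End of Treatment (Visit 5 or Day16) procedures"; those procedures include OSCI.

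**The concern.** Leaving hospital alive is among the better outcomes in this trial, yet the planned time-to-improvement can give it one of the longest times. If no decrease was present at Visit 5, and the subject goes home before the next required score, the SAP has nothing to date the improvement by until the Day 28 contact. A slower subject who is still in hospital on Day 16 is scored then and gets a shorter time.

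The summary of days would then partly describe the visit calendar. It could reverse the order of subjects and hide a difference between faster and slower recovery. It would also sit beside SAP 8.3.6, which would list the same subject's discharge on its true day. Identifying an early efficacy signal is a stated objective, so a descriptive summary that can run backwards matters even though nothing is tested.

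**Working it through.** The plan gives no figure of its own to reproduce, so the check is a mapping of discharge day to recorded day.

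**Inputs**
- Required post-baseline OSCI in Part 1: Visit 5 (about Day 5), Day 16 and Day 28 (Protocol 5.4.2).
- Day 28 contact for a discharged subject: 28 − 3 = Day 25 to 28 + 3 = Day 31 (Table 2, footnote 6).
- Appendix 1: scores 3 to 7 are hospitalized states, and 1 and 2 are ambulatory.
- Entry requires supplemental oxygen (Protocol 3.6 and 4.1), so baseline OSCI is 4 or more.

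**Delay**

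Take a subject discharged on day d after Visit 5, with no decrease at any earlier required score and no unscheduled score. Recorded day = 28 (25 to 31). Delay = 28 − d, with range 25 − d to 31 − d. The SAP's added 1 cancels.

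| Discharge day | Delay (days) | Range with call window |
|---|---|---|
| 6 | 28 − 6 = 22 | 19 to 25 |
| 8 | 28 − 8 = 20 | 17 to 23 |
| 12 | 28 − 12 = 16 | 13 to 19 |
| 15 | 28 − 15 = 13 | 10 to 16 |
| 20 | 28 − 20 = 8 | 5 to 11 |

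**Order of subjects**

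Subject A scores 4 at baseline and at Visit 5 and goes home on Day 8. Subject B has the same scores, comes off oxygen on Day 14 and is an inpatient scored 3 on Day 16. A went home 14 − 8 = 6 days before B improved. A is recorded at 28 and B at 16, so A looks 28 − 16 = 12 days slower. SAP 8.3.6 would show A discharged on Day 8.

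**Two-point decrease from baseline 4**

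4 − 2 = 2, which is an ambulatory state. An inpatient scores 3 or more, so no in-hospital assessment can record this event, however often it is done.

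**Effect on a group mean**

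SAP 8.1 provides for pooled and within-cohort comparisons. With 3 subjects in a cohort arm, all contributing a time, one subject dated 20 days late moves the mean by 20/3 = 6.7 days. In a pooled arm of 10 or 11 (assumed; the split of the 21 is not given) it moves the mean by 20/10 = 2.0 or 20/11 = 1.8 days.

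**Illustration**

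The assumptions here are not from the documents. All subjects improve after Day 5, with exponential times of median 3, 5, 8 or 12 further days. Discharge follows after an exponential lag of mean 2 days. There are no unscheduled scores, and the final contact is on Day 28.

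| Median further days | True mean, improved by Day 28 | Recorded mean | Improved by Day 16 but recorded at Day 28 |
|---|---|---|---|
| 3 | 9.2 | 27.2 | 93% |
| 5 | 11.2 | 27.0 | 90% |
| 8 | 12.9 | 26.9 | 87% |
| 12 | 14.0 | 26.9 | 85% |

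A true spread of 14.0 − 9.2 = 4.8 days shrinks to 27.2 − 26.9 = 0.3 days, and the fastest group has the longest recorded mean. The scenario contains only subjects not improved at Visit 5, so it shows the mechanism and not the expected size in this trial.

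**The case against.** A reader might infer that discharged subjects have no OSCI at all until Day 28, or that recorded times can fall only on about Day 5, 16 or 28. The documents do not support either. Unscheduled scores are collected when done. A subject discharged before Visit 5 should have an attempted End of Treatment score, so a 1-point decrease can be dated near discharge. The weekly calls are entered in the EDC, and whether they score OSCI is left open. What remains is that nothing requires a score between a discharge after Visit 5 and the Day 28 contact.

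A reader might also infer that a full daily OSCI can be rebuilt from data already held. That is not shown either. Table 2, footnote 1, records start times of oxygen therapy, and no stop date for low-flow oxygen is described. Score 7 needs organ-support data, and SAP 6.3 says that vasoactive use has no separate form.

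Appendix 1 never mentions discharge, so equating discharge with score 2 or lower is an inference. It is sound for a living subject who is no longer hospitalized, because scores 3 to 7 are all hospitalized states. The scale does not place someone sent home on oxygen.

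The Day 16 score rests on the text of Protocol 5.4.2. The OSCI row of Table 2 seems to show only one mark between baseline and the last, but the table could not be read reliably in the copy reviewed. If Day 16 were not required, the comparison with a Day 16 inpatient would fall away, and the gap between required scores would grow to 28 − 5 = 23 days.

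Finally, the consequence is modest: SAP 6.2 drops Kaplan-Meier estimates for this outcome, SAP 7.4 rules out inference, and SAP 8.3.7 also reports Yes/No improvement at Day 28 and lists all scores. That limits the harm but does not correct the day counts.

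**Conclusion.** The point holds in this limited form. For a subject discharged after Visit 5 without a recorded decrease, the plan as written can date improvement to about Day 28. The delay shrinks from about 22 days for a Day 6 discharge to 8 for Day 20. The 2-point outcome from baseline 4 is the worst case, because no inpatient score can show it.

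This assumes no unscheduled OSCI near discharge and no OSCI on the weekly calls. The documents give no distribution of discharge days, so the number of subjects affected is unknown. The outcome is secondary and descriptive in a 21-subject study stopped early. It deserves correction because the summary can mislead and the correction is cheap, but no test rests on it.

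**What to change.** In SAP 7.2 and 8.3.7, date the first 1- and 2-point decrease as the earlier of (a) the first OSCI record showing it and (b) the date of live discharge. With baseline 4 or more and discharge at 2 or lower, live discharge is a fall of at least 4 − 2 = 2 points, so one rule serves both outcomes. Flag any subject discharged on home oxygen. State whether unscheduled and Telemed scores count.

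If that is not wanted, drop the day counts. Report the proportions improved by Visit 5, Day 16 and Day 28, with live discharge counted as improved. Do not rely on a daily derived OSCI unless oxygen stop dates and organ-support dates are confirmed to be in the EDC.

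In the same edit, reconcile the reference score. SAP 7.2 defines the Yes/No decrease against OSCI at Day 28 (or End of Treatment), while SAP 8.3.7 measures it from baseline.

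The cost is a SAP paragraph and light programming on 21 subjects, since SAP 7.2 already derives time to discharge. The downside is that some improvement dates come from discharge and not from an investigator's score, so mark them in the listing.
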